take place. These surveys will take place in the community, for example, at day programs, group homes, or psychiatric rehabilitation agency offices where annual meetings take place. Potential participants who, after receiving a verbal summary of the project, including information about the survey, indicate they are interested in participating will have their de-identified survey response entered, including the study ID and question responses, into a secure, mobile, online database (REDCap). The Project Manager at each agency will track completed surveys in their database. In the event that a participant does not attend the scheduled IAP meeting or indicates that he or she would like to consider completing a survey at a later date, a Project Manager will attempt to reschedule the interview. Those who indicate they do not wish to answer the survey questions and do not wish to be asked again will have their study ID removed from the list of participants.

The master databases, one for each agency, will be housed at the respective psychiatric rehabilitation agencies. These will contain the study ID, name, address, primary care clinic, clinic randomization and CHW randomization status, assessment status at the Year 1, 2, and 3 assessment (complete, pending, refused) and any important instructions about contacting the client. This database will contain no study survey data and will not be available to MGH staff. The study database, housed at MGH only, will identify participants only with a study ID and will contain study-related data (Study ID, age at baseline assessment, sex, and survey question responses including smoking status, questions regarding smoking treatment in the prior year). These data will not be linked to or included in the master database.

At the end of the data collection period, the statisticians will receive two de-identified databases (one from each psychiatric rehabilitation agency, each including the study ID for each participant for merging purposes) and a de-identified database from MGH, also with each participant identified only by a Study ID. The statisticians will merge these two files using study ID as a common identifier and conduct statistical analyses to learn whether one or both of the intervention increased provision of smoking related treatment or rates of tobacco abstinence among survey participants.

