Indication of whether prescriptions were refilled
Limited set of patient study data
Study arm
Age group (ten year increments)
Gender
Self-reported smoking cessation medication use (varenicline, bupropion, NRT) at baseline, Y1, Y2
Race
Ethnicity
Self reported abstinence at Year 1 (baseline), Year 2 (intervention year 1), and Year 3 (intervention year 2)
The use of pharmacy data involves no more than minimal risk to participants. All PHI disclosed to MassHealth will be protected using secure transfer and storage and we will disclose the minimum amount of data necessary (e.g., IDs, intervention date windows, age groups) that pose minimal risk to participants. No PHI will be included in any of the data files received from MassHealth or analyzed by MGH staff and the de-identified data will be protected. Only aggregate results will be presented.

These data will be stored on Partners servers and behind the Partners Information Security firewall. Data will not leave the performance site and will not be stored on removable devices such as laptops or external drives. Access control to the data is maintained centrally via Active Directory, and will not be accessible to persons outside of the study team (access is by username and password authentication).

Request for Waiver of Written Consent

1) The proposed research involves no more than minimal risk to participants.

We propose to study the effects of enhancements to a system of usual care delivery on primary care provision of evidence-based ‘standard of care’ treatment for tobacco

addiction and smoking cessation rates. Patient safety will be overseen by primary care providers and the psychiatric rehabilitation team in the course of usual care.

Participants will be asked to respond to a brief 5-minute survey once a year for 3 years and may be offered CHW support as a supplement to their usual psychiatric rehabilitation supports, which they can either accept or decline, as they do for other psychiatric rehabilitation services, such as housing support and vocational support. Whether a person agrees to participate or not, their primary care clinic staff may receive academic detailing regarding safety and efficacy of standard of care smoking cessation treatment for people with psychiatric illness.

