Only aggregate results across groups of providers or patients will be analyzed and shared; no information on individual providers or patients will be generated or shared. We will not publish or report any cell size with 10 or fewer participants in accordance with data suppression policies.

V. STUDY PROCEDURES

This study aims to compare the effects of service interventions, AD+CHW, AD, CHW and TAU, on smoking outcomes in a large community psychiatric rehabilitation system of care.

Allocation concealment: Intervention allocation will be randomly assigned by computer generated list.

Blinding: Neither participants nor providers will be blind to the intervention assigned. Research coordinators who conduct the surveys with all participants will be blind to intervention assignment to the extent possible as the participant may volunteer information that makes study assignment clear to the coordinator.

1. Overview of Survey Visits:

Research assistants will attend the annual, scheduled CBFS and ACT rehabilitation team treatment planning meeting in the community to conduct an annual survey when the psychiatric rehabilitation team is engaging with the patient. The schedule of psychiatric rehabilitation team meeting is fixed according to the month of enrollment in CBFS or ACT, and the study assessments will accommodate this schedule. The brief annual survey will take 5 minutes for most participants. Those who complete the baseline survey will be asked to repeat the survey at their next two annual psychiatric rehabilitation team meetings.

2. Survey Items

2.1 **Demographics:** age, sex, race, living situation (Group Home/Supervised Housing or Independent Living) (Baseline Assessment only)

2.2 **Smoking Status:** If smoking: number of cigarettes smoked per day; if prior smoker: time since last cigarette and quitting method.

2.3 **Smoking cessation services in the past year:** If smoking: report of whether smoking status was assessed by their primary care physician or nurse, whether advice to quit smoking was given, whether prescription of pharmacotherapeutic cessation aids and/or referral to behavioral smoking cessation treatment were offered or made.

- If pharmacotherapeutic cessation aids were prescribed, we will ask if the was filled, and, if so, whether the medication was used, and, if so, for how long.

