- If behavioral smoking cessation support was recommended, we will ask if this support was used and, if so, what type (quit line, smoking cessation group or individual treatment) and how many sessions were attended.
- 2.4 If smoking: ***The Heaviness of Smoking Index*** (HSI) will be administered. It consists of 2 questions: time to first cigarette of the day and number of cigarettes smoked per day. The HSI and its individual items are strong predictors of quitting behavior, now validated in the International Tobacco Control cohort with 8,000 respondents/wave and 6,000 for prediction of cessation outcomes [75].
- 2.5 ***Health related quality of life***: The single item self-reported general health status question (SF-1) is well validated as a descriptor of individual health and wellbeing as well as community health status. [76] SF-1 scores are highly correlated with measures such as future health care use, mortality, disability, and mental health status [77-82] and SF-1 scores are significant indicators of health outcomes, independent of gender or racial/ethnic group. [78]
- 2.6 In those who report having quit smoking: Carbon monoxide in expired air, ***Expired CO***, will be measured with a small, hand-held CO monitor. To do so, participants will blow into a straw attached to the device, a Bedfont Smokerlyzer II (Kent, England), following a 15-second breath hold to verify self-report of non-smoking status. Expired CO <5 parts per million (ppm) is consistent with smoking abstinence.
 - We will measure cotinine in saliva in those whose expired CO is >5 ppm but report smoking zero cigarettes per day in the past 7 days and are not using nicotine replacement therapy. To do this, participants will provide a saliva sample via passive drool that will be tested with a NicAlert® dipstick (Nymox Corp., Hasbrouck Heights, NJ). The NicAlert® test displays seven zones that represent a range of cotinine levels from 0 (0–10 ng/ml) to 6 (> 1000 ng/ml). Participants that obtain a level between 1 (10–30 ng/ml) and 6 will be considered to be smoking

This is standard for biochemically verified abstinence and a critical component to obtaining reliable estimates of smoking status, the study's primary outcome, which will be used to judge the utility of the interventions being tested.

3. Interventions

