Exploratory Aim 3: Through data collected by the RAs for both AD+CHW and TAU groups, we will identify differences in care processes that will be suggestive of specific mechanisms. The main components of the intervention are i) AD to prescribers, which is designed to increase the number of smoking cessation interventions initiated including prescriptions written and referrals for behavioral treatment; and ii) the availability of CHW

support to patients and providers, which is intended to improve client engagement with prescriber recommended tobacco treatment, including increasing access to, and use of tobacco treatment pharmacotherapies and attendance at behavioral smoking cessation treatment. The CHW, through encouraging cessation attempts and through client support, is expected to increase the effectiveness of the pharmacotherapies and behavioral groups, and reduce relapse risk. We will conduct exploratory analyses examining differences in self reported prescriptions received, prescriptions filled, and smoking cessation groups attended by study arm using linear mixed effects models with clinic random effects.

Exploratory Aim 4. Hypothesis 4a: *Participants with schizophrenia and schizoaffective diagnoses will demonstrate lower absolute rates of biochemically-verified, 7-day point-prevalence tobacco abstinence than those with other diagnoses.* This rate will be compared between the two groups using generalized linear mixed models logistic regression.

Hypothesis 4b. *Participants with schizophrenia and schizoaffective diagnoses will a demonstrate larger effect of treatment (AD+CHW) vs no treatment (TAU).* This effect will be compared between the two groups using generalized linear mixed models logistic regression. These hypotheses are underpowered to detect an effect and are considered to be exploratory only.

Aim 5: We will use an interactive convergent design, as the emerging qualitative and quantitative data findings will inform respectively additional analyses. Our interactive intramethod approach or “iterative approach” will allow for us to generate hypotheses resulting from the qualitative data analysis which we will examine quantitatively using Year 3 data to further inform the joint display analysis.

Quantitative Data Analysis

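### As written, survey item 2.3 asks only current smokers about past-year cessation services, so Exploratory Aim 3's by-arm comparison of prescriptions and group attendance would be confined to continuing smokers, a post-randomisation group

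*Combined protocol and SAP*

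**What the plan says.** Section V.2, item 2.3 covers cessation services in the past year. It opens with a condition: "If smoking: report of whether smoking status was assessed by their primary care physician or nurse, whether advice to quit smoking was given". Whether a prescription or a behavioural referral was offered or made falls in the same sentence. The bullets beneath it ask about filling and using the medication and, for behavioural support, "what type (quit line, smoking cessation group or individual treatment) and how many sessions were attended".

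The separate branch for people who have stopped is in item 2.2: "if prior smoker: time since last cigarette and quitting method". What the method question records is not stated.

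Section VII.2, Exploratory Aim 3, uses data collected by the research assistants: "We will conduct exploratory analyses examining differences in self reported prescriptions received, prescriptions filled, and smoking cessation groups attended by study arm". No restriction to smokers is given. Section IV (Subject Enrollment) also says the merged data will be used to "learn whether one or both of the intervention increased provision of smoking related treatment or rates of tobacco abstinence among survey participants". Aim 1 in Section II opens by asking whether AD+CHW increases prescribers' advice and assistance to quit.

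Several passages do not carry the condition. Section IV describes the annual survey as covering how the primary care team dealt with smoking over the past year. The waiver request describes its primary-care questions in similar terms. The file for MassHealth lists "Self-reported smoking cessation medication use (varenicline, bupropion, NRT) at baseline, Y1, Y2", and the mediation analysis in Section VII.1 relates medication use to abstinence. Neither limits medication use to smokers.

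**The concern.** Smoking status at Years 2 and 3 is the trial's outcome, measured after randomisation, and the plan expects it to differ 3- to 6-fold between AD+CHW and TAU. Asking the service questions only of those still smoking removes a larger share of the AD+CHW arm than of the TAU arm. The people removed are those for whom treatment may have worked, and Aim 3 is meant to suggest mechanisms.

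A by-arm difference among continuing smokers then mixes the effect of the intervention on care with the effect of selection by outcome. The skipped answers are what would be needed to separate the two.

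The same condition removes quitters' reports of advice and referral. Those bear on Aim 1's opening question and on the Section IV statement about treatment provision. They are not among the variables Aim 3 names for its by-arm comparison.

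**Working it through.** **Inputs from the documents.** Planned abstinence, AD+CHW vs TAU: 15% vs 5% (Section VII.4), 16% vs 5% (Section VII.3, Table 1), 18% vs 3% (Table 2). Analysed sample: 900 (Section VII.4).

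**Assumption on arm size.** 900 / 3 = 300 per arm. Clinics are allocated one third to TAU and two thirds to AD, and clinic sizes vary, so equal arms are only approximate.

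**The plan's own quit rate.** Section VII.4 takes 65% attempting, 30% of those succeeding and 20% of successes relapsing: 0.65 × 0.30 × 0.80 = 0.156, in line with its 15%. If every quitter made an attempt, the share with an attempt among those still smoking is (0.65 − 0.156) / (1 − 0.156) = 0.494 / 0.844 = 58.5%, against 65% in the whole arm. On the plan's own figures, conditioning on smoking changes the group described.

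**People skipped by item 2.3** (300 × quit rate):

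| Planned rates | AD+CHW | TAU | Ratio |
|---|---|---|---|
| 15% / 5% | 45 | 15 | 3.0 |
| 16% / 5% | 48 | 15 | 3.2 |
| 18% / 3% | 54 | 9 | 6.0 |

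These rates plan for biochemically verified abstinence. The condition acts on self-report, so people who report quitting but fail verification would be skipped as well.

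**Bias.** In each arm let q be the quit rate, r service use in all participants, f in quitters and s in continuing smokers. Then r = q·f + (1 − q)·s, so s = (r − q·f) / (1 − q). The smokers-only difference minus the all-participant difference is q_T(f_T − s_T) − q_A(f_A − s_A), with A for AD+CHW and T for TAU. Its sign depends on f in both arms, which the survey as written does not record.

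**Illustration.** The documents give no service-use rates. Assume true prescription rates of 40% vs 25% (a 15-point effect) and 80% of TAU quitters prescribed.

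- At 15% / 5%, s_T = (0.25 − 0.04) / 0.95 = 0.221. With 80%, 60% or 50% of AD+CHW quitters prescribed, s_A = 0.28/0.85, 0.31/0.85 or 0.325/0.85 = 0.329, 0.365 or 0.382. The smokers-only difference is 10.8, 14.4 or 16.1 points.
- At 18% / 3%, s_T = (0.25 − 0.024) / 0.97 = 0.233. On the same three assumptions, s_A = 0.312, 0.356 or 0.378, and the difference is 7.9, 12.3 or 14.5 points.

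The bias can run either way. The effect keeps its sign in all six cases.

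**Bounds.** Assume the smokers-only result is 30% vs 30% at 15% / 5%. All-participant use is 0.255 + 0.15·f_A in AD+CHW and 0.285 + 0.05·f_T in TAU.

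- With f unrestricted, the difference lies between 0.255 − 0.335 = −8 points and 0.405 − 0.285 = +12 points. The width is q_A + q_T = 20 points (21 at either table's rates).
- If quitters in each arm were served at least as often as smokers, it lies between −0.05 × 0.70 = −3.5 and 0.15 × 0.70 = +10.5 points.

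**The case against.** The strongest reply is that the condition is a drafting slip. The survey is described twice without it, and the MassHealth file and the mediation analysis both use medication data not limited to smokers. If everyone was asked, the bias analysis does not apply. This is plausible and stands as a possibility. It does not dispose of the point, because item 2.3 then misstates who was asked. The Time and Events Table does not settle the matter: it lists the smoking questionnaire at every visit, but also lists the Heaviness of Smoking Index without condition, which item 2.4 gives only to smokers.

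Second, a reader might infer that quitters have no service data from any source. The documents do not support that. The method question in item 2.2 may show medication or group use. For covered participants, the MassHealth file holds fills and a claim-denial flag alongside study arm and self-reported abstinence. Neither is described as giving advice, referral, session counts or prescriptions never presented to a pharmacy.

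Third, a reader might infer that item 2.3 contradicts the cotinine rule, which applies to people who "report smoking zero cigarettes per day in the past 7 days and are not using nicotine replacement therapy". That is not shown. Item 2.6 has its own branch for people reporting that they quit, and it concerns current nicotine replacement, not past-year services. The MassHealth medication field could likewise be assembled from item 2.3 for smokers and the method question for quitters. These passages fit poorly with item 2.3 without being proven to conflict.

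Fourth, the service-use rates above are assumed, several illustrated biases are small, and Aim 3 is exploratory. All of that is correct and limits the weight of the point. Also, someone smoking at Year 2 and abstinent at Year 3 still supplies Year 2 answers, though only for the earlier year.

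**Conclusion.** The point holds on the text. Followed as written, item 2.3 confines Aim 3's three named self-report comparisons to continuing smokers, while the analysis is stated without that restriction. The result would not be a randomised contrast, and its bias has no known direction. About 45 vs 15, 48 vs 15 or 54 vs 9 people are skipped at the planning rates. This assumes 300 per arm and takes verified abstinence in place of self-report, so the true numbers would be higher.

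Three stronger readings are not supported. Advice, referral and session counts are not among Aim 3's named by-arm variables; losing advice and referral touches Aim 1's opening question and the Section IV statement instead. The 20-point width is a worst case, not an expected bias. The primary abstinence outcome does not depend on item 2.3 and is unaffected.

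The documents do not show whether the condition was applied in the field. Until that is stated, readers cannot tell which population the Aim 3 results describe. It should be corrected, but it is confined to process outcomes.

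**What to change.** Reconcile item 2.3 with the survey descriptions in Section IV, the MassHealth file and the mediation analysis, and state who was asked.

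- **If everyone was asked, or collection is still open:** delete the opening smoking condition from item 2.3, ask all participants at Years 2 and 3, and analyse the process outcomes in all randomised participants.
- **If only smokers were asked:** label the survey process results *among continuing smokers*, report the number of self-reported quitters excluded per arm, and give all-or-none bounds as above. Use the claims fills by arm already planned under Aim 1 as the medication comparison, in all covered participants. Reporting fills among quitters alone would breach the cell-size rules in Section IV: splitting 15 TAU quitters into filled and not filled leaves one cell of at most 7.
- **For the mediation analysis:** name a source of medication use obtained irrespective of smoking status.

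The cost is a corrected sentence; or a slightly longer survey for quitters, within a survey planned at five minutes for most participants; or a label, a count per arm and a short bounds calculation.

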Aim 1. Hypothesis 1a. *Those who receive AD+CHW will demonstrate higher rates of biochemically verified tobacco abstinence than those who receive usual care (TAU).* The primary outcome will be the proportion of smokers who are abstinent at their Year Three Assessment. This will be 12-24 months after randomization to study interventions because assessments are conducted in the pragmatic setting of the annual psychiatric rehabilitation team meetings. This smoking abstinence rate will be compared between the two groups using a generalized linear mixed models logistic regression, with random effect for clinic, assumed to be normally distributed [114]. **Hypothesis 1b.** *Those who receive AD+CHW will demonstrate higher rates of biochemically verified tobacco abstinence than those who receive AD only.* This rate will be compared between the two groups using logistic regression. **Hypothesis 1c.** *Those who receive AD will demonstrate higher rates of biochemically verified tobacco abstinence than those received TAU.* This rate will be compared between the two groups using generalized linear mixed models logistic regression. Hypothesis 1d. Participants assigned to receive CHW will demonstrate a higher rates of biochemically verified, 7-day point-prevalence tobacco abstinence than those assigned to TAU at the Year 3 Assessment. This will be tested with factorial analysis in the combined sample, using cohort as a factor. Additionally, we will compare MassHealth pharmacy claims data for smoking cessation medications (varenicline, bupropion and nicotine replacement therapy) to examine differences in prescribing patterns of providers randomized to AD compared to those randomized to TAU. We will also examine the effect of the interventions on rates of participants filling prescriptions for smoking cessation medication (i.e. AD, AD+CHW, CHW, TAU)

Aim 2: Hypothesis 2. *Those who receive AD+CHW will demonstrate improved Quality of Life compared to those who receive usual care, as assessed with the SF-1 (Overall Health).* We will assess this hypothesis with a random effects model with baseline, duration of follow up, and treatment group as covariates and a clinic random effect. We will use data from the last visit during the study as the dependent measure.

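### The CO cut-off for abstinence (below 5 ppm) and the trigger for saliva cotinine (above 5 ppm) do not meet, so a self-reported quitter at exactly 5 ppm is neither verified nor sampled

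*Combined protocol and SAP*

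**What the plan says.** Section VII.2 (Aim 1, Hypothesis 1a) states: "The primary outcome will be the proportion of smokers who are abstinent at their Year Three Assessment". The hypothesis requires that abstinence be biochemically verified, but the working definition appears only in Section V, Survey Items, item 2.6, for participants who report having quit. It has three parts:

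- CO test: "Expired CO <5 parts per million (ppm) is consistent with smoking abstinence".
- Cotinine trigger: "We will measure cotinine in saliva in those whose expired CO is >5 ppm but report smoking zero cigarettes per day" over the past week, with the added condition that they "and are not using nicotine replacement therapy".
- Cotinine result: "Participants that obtain a level between 1 (10–30 ng/ml) and 6 will be considered to be smoking". That level 0 clears a participant is implied but not written.

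The same item says that this verification is critical to "obtaining reliable estimates of smoking status, the study's primary outcome".

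**The concern.** The two CO conditions are strict inequalities on either side of the same number, so 5 ppm belongs to neither. Staff who follow the text will not take saliva from a non-NRT participant at 5 ppm. A participant at 6 ppm does get the cotinine test and can be cleared by it. The lower reading is thus treated less favourably than the higher one, which cannot be intended.

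The gap takes effect at the visit. If saliva is not collected that day, a later decision can only assign the case by rule. It cannot recover the measurement.

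A related but lesser matter is the NRT user who reports having quit and whose CO is not below 5 ppm. No cotinine test is ordered and no outcome is written down. At stake in both cases is how a small number of participants are counted in the primary comparison, and whether that was settled before the data were seen.

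**Working it through.** **1. Apply the rule at and around the cut-off.** For participants who report having quit and report no cigarettes in the past 7 days (item 2.6):

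| CO | Not using NRT | Using NRT |
|---|---|---|
| 4 ppm | abstinent | abstinent |
| 5 ppm | no rule, no sample | no rule, no sample |
| 6 ppm | cotinine test decides | no rule, no sample |

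The documents do not state the resolution of the monitor. If it reads in whole ppm (assumed), 5 is an ordinary attainable value.

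**2. Look for the missing rule elsewhere.** Section II and Section VII.2 require biochemical verification without defining it. The Time and Events Table lists exhaled CO only. The Missing data text imputes Year 3 outcomes for those without a Year 3 assessment, and does not address someone who attended but had no conclusive test. Nothing closes the gap.

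**3. Weight of one participant.** Arms are assumed equal, as one third of clinics go to TAU and half of the participants at the remaining clinics are offered a CHW.

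- Power calculation (VII.4): 900 / 3 = 300 per arm; 1/300 = 0.33 points.
- Enrolled Cohort 1 (III): 1165 − 155 = 1010; 1010 / 3 = 337. With 10% attrition a year for two years, 337 × 0.90² = 273; with 12%, 337 × 0.88² = 261. At about 270, 1/270 = 0.37 points.

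Three net reclassifications in one arm therefore make about one point (3 × 0.33 = 1.0; 3 × 0.37 = 1.1). The planned difference is 10 points in VII.4 (15% vs 5%) and 11 in the first row of Table 1 (16% vs 5%).

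**4. Reproduce the plan's power, then vary it.** Table 1, first row, gives 0.96 for TAU vs AD+CHW at ICC 0.03. Assume 300 per arm, 13 TAU and 27 AD clinics (40 split one third to two thirds), and a two-sided 0.05 test (the level is not stated). Effective n = 300 / [1 + (300/k − 1) × 0.03], which gives 180 for k = 13 and 230 for k = 27. Power = Φ[(d − 1.96 × SE₀) / SE₁], with SE₀ pooled and SE₁ unpooled: (0.11 − 1.96 × 0.0313) / 0.0291 = 1.67, so power is 0.953. That agrees with 0.96.

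The share of unresolved cases is not in the documents. As an illustration only, suppose that 5 to 20% of the 48 AD+CHW abstainers (16% of 300) fall in either empty cell, are all truly abstinent, and are all counted as smoking:

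| Assumed share | People of 48 | AD+CHW rate | Difference and power, same share in TAU | Difference and power, none in TAU |
|---|---|---|---|---|
| 0% | 0 | 16.0% | 11.0 points, 0.953 | 11.0 points, 0.953 |
| 5% | 2.4 | 15.2% | 10.45 points, 0.941 | 10.2 points, 0.927 |
| 10% | 4.8 | 14.4% | 9.9 points, 0.927 | 9.4 points, 0.891 |
| 20% | 9.6 | 12.8% | 8.8 points, 0.890 | 7.8 points, 0.781 |

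The bottom row needs nearly ten such people in one arm and none in the other. Nothing in the documents suggests that this is likely.

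**The case against.** The best defence is that the outcome is verified abstinence, so anyone not verified is by ordinary meaning not abstinent. On that reading nobody is left without a classification, and the text is merely terse. This largely stands for NRT users. Cotinine is withheld from them on purpose, since a positive result could not separate NRT from smoking. Using NRT does not by itself put anyone in the gap, because an NRT user below 5 ppm is classified as abstinent. For one who is not below 5 ppm, CO and NRT status are both recorded, so the classification can be made at any time.

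The defence is weaker for a non-NRT participant at 5 ppm. The default would count that person as smoking without the second test that is given at 6 ppm, and the sample that could have settled the matter was never taken.

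A reader might go further and infer that the primary endpoint is undefined, that the gap could move the result in either direction, or that unresolved NRT cases will be more numerous in the intervention arms. The documents do not support these. The natural default points one way, towards not abstinent. The affected NRT users must report having quit, be using NRT at the visit, and fail to read below 5 ppm; no figure bears on that joint frequency. The interventions promote bupropion and varenicline as well as NRT, so the most that can be said is that NRT use may differ between arms.

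**Conclusion.** The threshold mismatch is real and follows from the literal text: at exactly 5 ppm a self-reported quitter not using NRT is neither verified nor sampled, and no other section repairs this. It is a minor defect in the definition of the primary outcome. Each case is worth 0.33 to 0.37 points in an arm of 300 to 270, assuming equal arms and the plan's own attrition. The frequency is unknown, but the effect is probably a few participants at most, against a planned difference of about 10 points. Only the saliva sample at 5 ppm is beyond recovery. The NRT matter is a clarification worth writing down, not a second error: the implied default is reasonable, but it should be stated, because NRT use may differ between arms.

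**What to change.** In item 2.6, change the cotinine trigger from CO above 5 ppm to CO of 5 ppm or more, so that the two thresholds meet. Make the same change on the survey form.

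The document is dated September 2021 and Section VII.1 describes some analyses in the past tense, so visits may be over. In that case, state before the primary analysis, or disclose if it has been run, that a self-reported quitter at 5 ppm without cotinine is not verified abstinent in every arm. Add a sensitivity analysis that counts these cases as abstinent.

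As a clarification, add that self-reported quitters using NRT with CO of 5 ppm or more are unverified and counted as not abstinent in every arm, with a sensitivity analysis that accepts their self-report. Report the number of participants in each cell by arm.

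The cost is an occasional extra use of a dipstick already in the protocol and a few sentences of text. The drawback is that a few true quitters on NRT may be counted as smokers. They have no second test, whereas non-NRT participants do, which is why the sensitivity analysis is needed.
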